Primary Hypothesis:

Our hypothesis is that internal, controlled transverse fracture compression with modern intramedullary rod treatment of transverse tibial shaft fractures will be associated with an increased rate and time to union compared to the traditional methods of dynamic locking and backslapping.

Methods:

Inclusion Criteria

1. Skeletal Maturity
2. Closed or open diaphyseal (shaft) tibia fracture that is axially stable and will tolerate compression without shortening.
3. Treatment with Intramedullary Rod.
4. Fracture compression using one of three methods:
 - a. Dynamic locking.
 - b. Backslapping with dynamic locking.
 - c. Internal rod compression with static locking.
5. Complete inpatient and outpatient medical records and operative notes.
6. Complete radiographic and clinical follow-up for minimum one year.

Exclusion Criteria

1. Skeletally immature.
2. Metabolic Bone Disease
3. Immunosuppression
4. Pathological Fracture (Tumor, Pre-existing Infection)
5. Pre-existing Infection
6. Soft-tissue coverage not obtained within two weeks from time of injury.
7. Use of Negative Pressure Dressing to definitively manage wound.
8. Use of external or implantable bone growth stimulator.

9. Unable to Full Weight Bear immediately post-operative.

Data Points:

1. Age
2. Sex
3. Medical Comorbidity
4. Smoking Status (Yes or No)
5. Closed or Open fracture:
 - a. Wound Size (surface area)
 - b. Wound type (Gustilo Anderson and OTA)
6. Number of Surgical Debridements
7. Time to definitive closure.
8. Soft Tissue Reconstructive Procedure
9. Compartment Syndrome (Yes or No)
10. Fasciotomy (Yes or No)
11. Treatment Method:
 - a. Dynamic locking.
 - b. Backslapping with dynamic locking.
 - c. Internal rod compression with static locking.
12. Union (Yes or No)
13. Time to union (months).
14. Implant complications (Rod or Screw Breaking)
15. Loss of reduction and healing alignment on orthogonal radiographs.
16. Need for subsequent secondary treatment:
 - a. Superficial Infection (Antibiotic Treatment)
 - b. Deep Infection (Surgical Treatment)
 - c. Delayed Union (Exchange rodding, Bone grafting)
 - d. Nonunion (Exchange rodding, Bone grafting)

Methodology:

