This study will be a prospective analysis of patients with transverse tibial shaft fractures (OTA 42-A3 classification) treated with an intramedullary rod. Patients will be enrolled at a single facility (Harborview Medical Center-HMC). Patients who meet inclusion criteria will be assigned to one of the three treatment groups based on the night of presentation. Currently there are three teams that manage the trauma call at HMC (Red, Green, Blue) and alternate on a strict 1 in 3 rotation schedule. Patients that present on a night when the Red Team is on call will be treated as Group A (dynamic locking). Patients that present on a night when the Green Team is on call will be treated as Group B (backslapping with dynamic locking). Patients that present on a night when the Blue Team is on call will be treated as Group C (internal rod compression). All three methods of treatment are considered acceptable current standards of practice in the orthopedic trauma community on a local and national level. All patients will be treated similarly with respect to:

1. Open wound management
2. Immediate post-operative full weight bearing.
3. Follow-up at 6 weeks, 12 weeks, 24 weeks and 52 weeks.
 - a. Radiographic
 - b. Clinical

Union will be determined according to the modified Hammer criteria,⁶ with union considered to have occurred with bridging cortical bone on 3 or 4 cortices using orthogonal radiographic views.

Risks

There is no risk to the patient as all three treatment methods are current standard of practice both nationally and locally. All patient identifiers will be kept private. All data will be stored on a password protected database available only to the study team.

Benefits

The study performed will provide information regarding the optimal treatment strategy for transverse tibia fractures, and what the expected time to union is when using internal

compression. This information is of benefit to patients, particularly when being counseled by surgeons regarding how long they can expect before obtaining radiographic union, and what the potential reoperation rate would be.

Procedures to Ensure Confidentiality

No patient identifiers will be used during the formal study. Identifiers such as name and medical record numbers will be used to identify patients with a transverse tibia fracture, and will be stored on a password protected departmental network in a master file. Data files will be listed with subject number.

Statistical Analysis Plan

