Descriptive statistics will be presented as means and standard deviations for continuous variables and as frequencies and percentages for categorical variables. Statistical analysis of categorical variables utilized Fischer's exact test with descriptive statistics reported as frequencies and percentages. For continuous variables, a Mann-Whitney U test was utilized with descriptive statistics reported as means and ranges. Significance set at p value less than or equal to 0.05. All statistical analyses were performed using IBM SPSS version 22 (Chicago, IL, 2013).

Bibliography:

1. Randomized Trial of Reamed and Unreamed Intramedullary Nailing of Tibial Shaft Fractures. *J Bone Joint Surg Am.* 2008;90:2567-2578.
3. Court-Brown CM. Reamed Intramedullary Tibial Nailing: An Overview and Analysis of 1106 Cases. *J Orthop Trauma.* 2004;18:96-101.
4. Blachut PA O'Brien PJ, Meek RN, Broekhuyse HM. Interlocking Intramedullary Nailing With and Without Reaming for the Treatment of Closed Fractures of the Tibial Shaft. *J Bone Joint Surg Am.* 1997;79:640-646.
6. Hammer RR Hammerby S, Lindholm B. Accuracy of Radiographic Assessment of Tibial Shaft Fracture Union in Humans. *Clin Orthop Relat Res.* 1985;199:233-238.

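### Each compression method belongs to one call team throughout, so the trial cannot separate the effect of the method from the effect of the team

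*Combined protocol and SAP*

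**What the plan says.** The Methodology section describes "three teams that manage the trauma call at HMC (Red, Green, Blue) and alternate on a strict 1 in 3 rotation schedule". It then states: "Patients who meet inclusion criteria will be assigned to one of the three treatment groups based on the night of presentation". The pairing is one to one. Red nights are Group A (dynamic locking), Green nights are Group B (backslapping with dynamic locking), and for Blue, "Patients that present on a night when the Blue Team is on call will be treated as Group C (internal rod compression"). There is one enrolling facility. No section moves a method to another team, randomises within a team or adds a second site.

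The same section says "All patients will be treated similarly with respect to" three things: open wound management, immediate weight bearing and the follow-up schedule. It also gives one radiographic definition of union for all groups. Neither team nor surgeon appears in the Data Points list. The Statistical Analysis Plan uses Fisher's exact test for categorical outcomes and, for the rest, says: "For continuous variables, a Mann-Whitney U test was utilized with descriptive statistics reported as means and ranges". Neither test includes a team term.

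The Primary Hypothesis is about the method: controlled compression "will be associated with an increased rate and time to union compared to the traditional methods of dynamic locking and backslapping". The Benefits section adds: "The study performed will provide information regarding the optimal treatment strategy for transverse tibia fractures".

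**The concern.** A strict rota may give the three groups similar patients. It cannot make the teams similar, because each arm has exactly one team. Anything that differs by team and affects union travels with the method. Operative technique and the decision to reoperate are not among the items to be held similar. Reoperation matters here because exchange rodding and bone grafting for delayed union or nonunion are themselves recorded outcomes (Data Points, item 16).

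The trial would therefore show whether Blue using internal compression does better than Red using dynamic locking or Green using backslapping. It would not show whether internal compression does better. This is a bias that the data cannot reveal, and enrolling more patients does not reduce it.

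**Working it through.** The plan states no sample size, expected union rate or power, so there is no figure of its own to reproduce. The check has an exact part and a conditional part.

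**1. Identifiability (follows from the assignment rule alone).** Take a model with an intercept, two team indicators and two method indicators, which is 5 columns. Under the rule in Methodology:

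| Team | Method | Intercept | Green | Blue | B | C |
|---|---|---|---|---|---|---|
| Red | A | 1 | 0 | 0 | 0 | 0 |
| Green | B | 1 | 1 | 0 | 1 | 0 |
| Blue | C | 1 | 0 | 1 | 0 | 1 |

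The Green column equals the B column and the Blue column equals the C column. The rank is 3 of 5, so no method contrast is estimable given team. Adding a team term to the planned tests would not help, because it is the method term.

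If instead the methods rotate over the teams in a 3×3 Latin square (three periods, each team using each method once), the columns are 1 + 2 team + 2 method + 2 period = 7, and the rank is 7 of 7. Residual degrees of freedom for team-by-period variation are:

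- one square: 9 cells − 7 = 2
- two squares (six periods): 18 − (1 + 2 + 2 + 5) = 8
- three squares (nine periods): 27 − (1 + 2 + 2 + 8) = 14

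**2. Limit on precision (assumed team SD).** Let σ be the between-team SD of the log-odds of union. The estimated log odds ratio between two arms is the method effect, plus the difference of two team effects, plus sampling error. Its variance is 2σ² plus a sampling term that goes to zero as patients are added. The SE therefore cannot fall below √2·σ, and the 95% range of odds ratios from teams alone extends to exp(1.96·√2·σ) or its reciprocal.

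| σ (assumed) | Union at ±1 SD around 85% | SE floor √2·σ | Upper 95% odds ratio |
|---|---|---|---|
| 0.2 | 82–87% | 0.28 | 1.7 |
| 0.3 | 81–88% | 0.42 | 2.3 |
| 0.5 | 77–90% | 0.71 | 4.0 |

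**3. False-positive rate of one pairwise Fisher test, no method effect.** Inputs: significance at p ≤ 0.05 (Statistical Analysis Plan), two-sided (assumed, since the plan does not say). Union rate, patients per arm and σ are also assumed. The rejection probability is enumerated exactly over both binomial counts and averaged over normal team effects on the log-odds scale.

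| Union | Per arm | σ = 0 | σ = 0.2 | σ = 0.3 | σ = 0.5 |
|---|---|---|---|---|---|
| 85% | 30 | 1.7% | 2.6% | 4.0% | 8.9% |
| 85% | 50 | 2.4% | 4.4% | 7.1% | 16.0% |
| 85% | 100 | 3.3% | 8.1% | 14.3% | 29.1% |
| 90% | 30 | 0.9% | 1.4% | 2.1% | 5.0% |
| 90% | 50 | 1.8% | 2.9% | 4.6% | 10.7% |
| 90% | 100 | 2.9% | 6.1% | 10.4% | 22.5% |
| 95% | 50 | 0.7% | 1.1% | 1.6% | 4.0% |

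Fisher's test is conservative, so with small arms, high union or little team variation there may be no excess over 5%. Where team variation exists, the rate rises with the number of patients.

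**The case against.** The strongest reply is that no team effect has been shown. The calendar rota should give comparable patients, union has a common definition, some care is standardised, and the hypothesis speaks only of association. The documents do not say that the presenting team operates. If another team does, the confounding weakens. They also speak of the teams as they currently stand, so a pairing fixed for the whole trial is inferred from the absence of any rule to change it. All of this is fair, but none of it separates method from team. A common definition of union does not equalise technique or reoperation decisions, no independent reader is stated, and without team or surgeon in the data set any crossing between teams could be neither shown nor used.

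Three narrower points stand:

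- The rank result is exact for assigned method. Treatment Method is a separate data point (item 11), and departures from assignment would break the exact aliasing for method received. That comparison would carry its own selection bias.
- Equal teams is a necessary condition for attribution to compression, not a sufficient one. Group C also uses static locking while A and B use dynamic locking, so breaking the team pairing identifies the effect of the compression-plus-locking method as a whole.
- The false-positive figures are illustrations. At σ = 0.2 there is no excess over 5% with 50 per arm at either 85% or 90% union.

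The past tense in parts of the Statistical Analysis Plan suggests that redesign may no longer be possible. That changes which remedy applies, not whether the problem exists.

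**Conclusion.** The concern holds, and it must be fixed because it affects the main comparison. Assigned method and on-call team are fully aliased (rank 3 of 5). This follows from the assignment rule and single-site enrolment, with no numerical assumption. As written, the trial compares team-plus-method packages, and neither more patients nor a different test changes that.

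The size of the possible error is unknown, because the documents give nothing on team variation. For an assumed SD of 0.3 to 0.5 on the log-odds scale, teams alone could produce odds ratios up to 2.3 to 4.0 in either direction. At 85% union, the false-positive rate of a single pairwise test would be 4–9% with 30 per arm, 7–16% with 50 and 14–29% with 100. The verdict rests on the lack of identifiability and does not depend on these figures.

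**What to change.** If enrolment can still be changed, break the fixed pairing in one of two ways.

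1. **Rotate by calendar.** Keep assignment by call night, but move the three methods across the three teams on a pre-set schedule: a 3×3 Latin square, preferably repeated over several short periods. Analyse union and time to union with models containing method, team and period main effects. Do not stratify by team-period cell, since each cell holds only one method.
2. **Randomise patients within team.** Replace call-night assignment with a concealed patient-level list stratified by team. Use a Cochran-Mantel-Haenszel test for union and a van Elteren test for time to union, both stratified by team, and state in advance how patients who never unite are ranked.

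Either way, add team (and period, if rotating) to Data Points, and replace or supplement the unadjusted tests. Recording the operating surgeon as well would show whether surgeons cross teams.

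The cost is an amendment to three places: the assignment paragraph in Methodology, the Data Points list and the Statistical Analysis Plan. No extra patients are needed to make the method contrast estimable, although precision cannot be checked without a planned sample size. Each team would have to use all three methods, which the protocol supports: "All three methods of treatment are considered acceptable current standards of practice in the orthopedic trauma community on a local and national level". Changeovers need managing under rotation, and a single square leaves only 2 residual degrees of freedom. Rotation also assumes additive effects and leaves the upcoming method predictable. Only the concealed list deals with predictability.

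If accrual is complete or the pairing must stay, state in the hypothesis and conclusions that team-plus-method packages are compared, and do not attribute differences to compression alone. This costs almost nothing. Abstracting the operating surgeon from the operative notes and re-reading radiographs blind to group would help judge how plausible equal teams are, but would not remove the aliasing.

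### The plan gives no value, rank or censoring rule for a patient who has not united, so its Mann-Whitney comparison of time to union, as written, can use only united patients

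*Combined protocol and SAP*

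**What the plan says.** - **Primary Hypothesis.** Internal compression "will be associated with an increased rate and time to union compared to the traditional methods of dynamic locking and backslapping". Union rate and time to union are thus both primary. The wording speaks of an increased time; I take the intended direction to be earlier union, as the Introduction's rationale implies.
- **Data Points.** Item 12 records union as yes or no. Item 13 separately records time to union in months. Item 16 provides for delayed union and nonunion, each treated by exchange rodding or bone grafting, so failure to unite is an expected outcome.
- **Methodology.** Union is bridging of three or four cortices on orthogonal films. The schedule is "Follow-up at 6 weeks, 12 weeks, 24 weeks and 52 weeks".
- **Inclusion Criterion 6.** "Complete radiographic and clinical follow-up for minimum one year".
- **Statistical Analysis Plan.** Categorical variables go to Fisher's exact test. For the rest: "For continuous variables, a Mann-Whitney U test was utilized with descriptive statistics reported as means and ranges".
- **Benefits.** The study is to tell patients "what the expected time to union is when using internal" compression.

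No section names a time-to-event method or a rule for a patient still not united.

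**The concern.** A rank test needs a value or a rank for each patient. A patient recorded as not united has neither, so the software drops that patient from the time comparison. The patients who remain are selected by the outcome that the treatment is meant to change.

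Two consequences follow. If one technique heals fractures uniformly faster, its additional unions enter at the slow end of its distribution and hide much of its advantage. If its benefit is mainly to convert nonunions into late unions, it can look slower on time while Fisher's test favours it, and the two halves of the hypothesis then point in opposite directions.

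The reported mean has the same fault as a counselling figure: it leaves out everyone unhealed at one year.

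A related gap is that the plan does not say whether a union reached only after exchange rodding or bone grafting counts as union in item 12, or what time it receives in item 13.

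The four-visit schedule also produces many ties and imprecise means, but that does not bias one arm against another.

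**Working it through.** **Inputs.** The documents give the visits (6, 12, 24, 52 weeks), the significance level (0.05, taken as two-sided) and the tests. They give no union rate, effect size or sample size, so there is no figure of the plan's to reproduce and every rate below is assumed. Comparisons are between two arms.

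**Step 1: a count that can be checked by hand.** Assume 20 patients per group.

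| Union at | 6 wk | 12 wk | 24 wk | 52 wk | never |
|---|---|---|---|---|---|
| Group A | 1 | 7 | 7 | 1 | 4 |
| Group C | 1 | 7 | 7 | 4 | 1 |

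Group C has three more unions and is otherwise identical.

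- Mean among the united: A = (6 + 84 + 168 + 52)/16 = 19.4 weeks; C = (6 + 84 + 168 + 208)/19 = 24.5 weeks.
- Mann-Whitney among the united, ties counted one half: U = 0.5 + 7 × 4.5 + 7 × 11.5 + 17 = 129.5. P(A later than C) = 129.5/(16 × 19) = 0.43, so C looks slower (p = 0.43).
- Nonunion ranked last: U = 129.5 + 4 × 19.5 = 207.5. P(A later than C) = 207.5/400 = 0.52 (p = 0.84).

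Neither result is significant, but the direction reverses.

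**Step 2: uniformly faster healing.** Exponential healing, hazard ratio 1.6, 50 per arm, 6,000 simulated trials per case. Union in the better arm is 1 − (1 − control union)^1.6.

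| Control v better arm, union at 52 wk | 70 v 85.4% | 80 v 92.4% | 90 v 97.5% |
|---|---|---|---|
| Mann-Whitney, united only | 13% | 18% | 29% |
| Mann-Whitney, nonunion last | 47% | 50% | 50% |
| Log-rank, all patients | 52% | 56% | 59% |
| Fisher, union yes/no | 39% | 33% | 17% |

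Wrong-direction significance was 0.5% or less. With no effect, the Mann-Whitney and log-rank tests rejected in 4.8% to 5.3%.

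**Step 3: late unions replace nonunions.** Both arms unite 5%, 25% and 30% at 6, 12 and 24 weeks; the remaining 40% divides between union at 52 weeks and nonunion. For 20% nonunion the mean among the united is (0.05 × 6 + 0.25 × 12 + 0.30 × 24 + 0.20 × 52)/0.80 = 20.9/0.80 = 26.1 weeks. For 5% it is (10.5 + 0.35 × 52)/0.95 = 30.2 weeks. The better arm shows the longer mean.

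| Nonunion, worse v better arm | United-only test significantly favours the worse arm, n = 30 / 50 / 100 per arm |
|---|---|
| 20% v 5% | 11% / 16% / 31% |
| 15% v 5% | 7% / 10% / 15% |
| 10% v 5% | 4% / 5% / 6% |

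The nominal rate is 2.5%. Log-rank on all patients did this in about 1.3% or less. In the 20% v 5% case Fisher's test favoured the better arm in 24% / 51% / 89%.

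**Step 4: the mean as a counselling figure.** Exponential healing, 70% united at 52 weeks: the visit probabilities are 0.130, 0.113, 0.184 and 0.274, and the sum of probability × week is 20.77. Among the united: 20.77/0.70 = 29.7 weeks. Counting the others at 52 weeks: 20.77 + 0.30 × 52 = 36.4 weeks. By the same method the pairs are 27.7 and 32.6 at 80% united, 24.6 and 27.3 at 90%, and 21.8 and 23.3 at 95%.

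**Step 5: union after secondary surgery.** Suppose 20% v 5% fail to unite by the assigned technique and three quarters of those unite after a second operation within 52 weeks. Union is 80% v 95% if these are not counted. If they are, it is 80 + 0.75 × 20 = 95% v 95 + 0.75 × 5 = 98.75%.

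**The case against.** The strongest reply is that the plan is silent rather than wrong. It does not say that nonunions are dropped, and one sentence ranking them last would let the Mann-Whitney test use every patient. That is true: the defect is the missing rule, not the choice of a rank test. But a silent plan leaves a blank value, and a blank value is excluded.

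Fisher's test does count nonunions, so the trial's overall loss is smaller than the loss in the time comparison. In step 2, either planned test finds the benefit in about 46%, 45% and 39% of trials, against 53%, 56% and 57% for log-rank in the same runs: a shortfall of 7 to 18 points, before any allowance for testing twice. Fisher's test does not, however, answer how fast fractures heal.

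The reversal needs a particular pattern. The Introduction expects more rapid healing, and under uniformly faster healing the direction is not reversed. If unions after reoperation are counted, so that 5% v 1.25% remain un-united, the wrong-direction rate in step 3 is only about 4% to 5%. The large reversal figures therefore apply only with late benefit and a wide gap in nonunion.

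The one-year follow-up criterion limits dropout by selecting completers, but gives no time to a completer who has not united. Ranking last suits only completers; a patient lost before 52 weeks cannot be ranked last without a further assumption, whereas censoring can include that patient.

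**Conclusion.** The concern holds and should be fixed. A primary endpoint has no rule for an outcome that the protocol itself expects. For the time comparison alone, the united-only test gives up roughly 20 to 40 percentage points of power under uniformly faster healing at 50 per arm. Reversal ranges from serious (up to 31% at 20% v 5% nonunion and 100 per arm) to slight (4% to 6% at 10% v 5%), and arises only if the benefit is late. The mean quoted to patients is too short by 1.5 weeks at 95% united and 6.7 weeks at 70%, even with the un-united counted only to 52 weeks. The gap in the text is certain; these sizes depend on assumed rates, arm sizes and healing patterns. Because Fisher's test still compares union rates on all patients, the flaw does not invalidate the trial.

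**What to change.** 1. Analyse time to union in all assigned patients, censoring those not united at their last scheduled film. Use Kaplan-Meier with a log-rank test, or a discrete-time (complementary log-log) model on the four visits.
2. As a minimum, add one sentence ranking nonunion last in the Mann-Whitney test, for patients with complete one-year follow-up.
3. Report cumulative union at each visit with 95% confidence intervals in place of the mean and range among the united.
4. State how union after exchange rodding or bone grafting is counted in items 12 and 13, for example as not united by the assigned technique through 52 weeks, and record the date of that surgery.
5. Keep Fisher's test on union.

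The cost is SAP wording, one standard method and one added date; union status and time are already collected. There are two drawbacks. The discrete-time model assumes proportional hazards across the four visits. If all benefit comes after 24 weeks, log-rank and rank-last have little power (18% and 8% at 50 per arm for 20% v 5% nonunion), which is why Fisher's test must stay.

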Union Rate of Transverse Tibia Fracture

NCT03042533

Date: 09.05.23

Union Rates of Transverse Tibia Fractures Managed with Internal Fracture Compression Through an Intramedullary Rod Compared to Standard “Backslapping”

[name]

Introduction

When compared to other fracture patterns, transverse fractures of the tibial shaft have historically been associated with an increased incidence of delayed union and nonunion when stabilized with intramedullary rods, perhaps due to the decreased cortical surface area available for healing.¹⁻⁴ As a result, some authors have recommended that simple transverse fractures of the tibial shaft be managed with plate fixation and compression of the fracture using an articulated dynamic tensioner.⁵ Open plating of the tibia requires a large incision which may be at an increased risk for soft tissue complications, particularly when operating through a high-energy injured soft tissue envelope. Furthermore, intramedullary rodding of the tibia is currently regarded as the gold standard for surgical management of tibia fractures, including transverse fractures, and as such compression plating is not considered a reasonable option unless other mitigating circumstances exist.¹

In recent years, technological advances in the design of intramedullary rods allow intraoperative, controlled compression of fractures with internal devices built in to the rod. This type of controlled compression may be beneficial when compared to traditional “backslapping” techniques, in which the amount of compression cannot be controlled or “dialed” in. After internal compression, static or dynamic locking of the rod can be accomplished as is routine when rodding typical long bone fractures. This advance poses a potential advantage when managing transverse fractures, the one fracture type most amenable to intraoperative compression to facilitate rapid bony healing.

The literature regarding intramedullary rodding of transverse tibia fractures is limited, and no literature exists comparing controlled internal compression with traditional methods of dynamic rodding or backslapping. The purpose of this analysis is to prospectively assess a consecutive cohort of patients with transverse tibial shaft fractures treated with intramedullary rodding and compressed with one of three methods: dynamic locking alone, backslapping followed by dynamic locking locking, or controlled internal

fracture compression with modern nails followed by static locking.

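### Time to union falls under a two-group test at an unadjusted 0.05 in a three-arm trial, with no rule for which comparison counts; if either does, the error is about 9%

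*Combined protocol and SAP*

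**What the plan says.** - **Arms.** Under Methodology, patients are "assigned to one of the three treatment groups based on the night of presentation". The on-call team, on a one-in-three rotation, decides the arm: dynamic locking (A), backslapping with dynamic locking (B) or internal rod compression with static locking (C).
- **Hypothesis.** Under Primary Hypothesis, internal compression "will be associated with an increased rate and time to union compared to the traditional methods of dynamic locking and backslapping". That is two outcomes and two comparators.
- **Other statements of the comparison.** The Introduction names the same two comparators: "no literature exists comparing controlled internal compression with traditional methods of dynamic rodding or backslapping". The title begins "Union Rates of Transverse Tibia Fractures Managed with Internal Fracture Compression Through an Intramedullary Rod Compared to Standard" and then names backslapping alone.
- **Outcomes.** Data Points lists union (yes or no) as item 12 and time to union in months as item 13.
- **Tests.** The Statistical Analysis Plan is one paragraph. It gives Fisher's exact test for categorical variables. For the rest it says "For continuous variables, a Mann-Whitney U test was utilized with descriptive statistics reported as means and ranges" and "Significance set at p value less than or equal to 0.05".

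The SAP does not name time to union. It does not say which groups the Mann-Whitney test compares, whether A and B are pooled, whether a three-group test comes first, or how more than one test is handled. It names no main outcome.

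**The concern.** A two-sample test cannot be applied to three arms until someone decides which two samples are meant. The hypothesis narrows this to C against A and B, but it leaves three workable rules: C is tested against each and either result supports the claim; C must beat both; or A and B are combined into one comparator group. These rules give the same p ≤ 0.05 quite different false-positive rates. Only the first pushes the error above the stated level, and nothing in the SAP excludes it. If the rule is chosen after the results are known, a reader cannot tell what error rate a significant result carries.

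**Working it through.** **Inputs from the documents.** Per-test level 0.05; three arms; comparisons C vs A and C vs B; team rotation one in three, so roughly equal arms are plausible but not stated. The plan gives no sample size, power or effect size, so apart from the chosen 0.05 there is no figure to reproduce.

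**Step 1: correlation between the two tests.** Both use arm C, so they are not independent. With A and B each of size n and C of size n_C,

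ρ = (1/n_C) / (1/n_C + 1/n) = n / (n + n_C).

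Equal arms give ρ = 0.5. If C is half the size of the others ρ = 0.667; if twice the size, ρ = 0.333.

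**Step 2: either comparison counts.** With no true difference and each test two-sided at 0.05,

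P(at least one false positive) = 1 − P(|Z₁| < 1.96 and |Z₂| < 1.96),

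where Z₁ and Z₂ are bivariate normal with correlation ρ.

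- ρ = 0.5: 0.0907
- ρ = 0.667: 0.085
- ρ = 0.333: 0.095
- For reference, independent tests give 1 − 0.95² = 0.0975, and the upper bound is 2 × 0.05 = 0.10.

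**Step 3: C must beat both.** With all arms equal, P(both significant) = 0.05 + 0.05 − 0.0907 = 0.0093. If C truly differs from one comparator only, a false claim still needs the other test to be falsely significant, so the error is at most 0.05.

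**Step 4: A and B pooled.** This is one test, so the error is 0.05.

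**Step 5: check on Mann-Whitney itself.** Null simulations used 20 and 40 patients per arm (assumed), with continuous data and with data tied at the four visits, 10,000 runs each. A wider set used 15 to 100 per arm and 80% to 95% union (assumed), with patients not united ranked last.

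| Rule | Normal theory | Simulated, 20 and 40 per arm | Simulated, wider set |
|---|---|---|---|
| Either counts | 0.091 | 0.087 to 0.091 | 0.086 to 0.093 |
| Pooled | 0.050 | 0.047 to 0.052 | 0.047 to 0.053 |
| Both, all arms equal | 0.009 | 0.009 to 0.010 | not run |

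**Step 6: does adjustment work, and what does it cost?** Testing each comparison at 0.05/2 = 0.025, the first step of Holm, gave 0.043 to 0.049 at 20 and 40 per arm. In the wider set full Holm gave 0.042 to 0.048, and a Kruskal-Wallis test at 0.05 before the pairs gave 0.046 to 0.052.

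For power, take an effect that gives C vs A 80% unadjusted: expected Z = 1.960 + 0.842 = 2.802. At 0.025 the critical value is 2.241, so that step alone gives Φ(2.802 − 2.241) = Φ(0.561) = 0.71. Holm adds the cases in which C vs B passes at 0.025 and C vs A then passes at 0.05. Normal theory with equal arms gives:

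| Power for C vs A | Unadjusted | Holm | Three-group test first |
|---|---|---|---|
| A equals B | 80% | 76% | 76% |
| B midway between A and C | 80% | 72% | 70% |

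**The case against.** Three objections have force.

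1. The hypothesis joins its comparators with an *and*. Read literally, C must do better than A and better than B, and then each test at 0.05 is sufficient. That reading is natural and the arithmetic supports it. It does not close the gap, because the SAP does not adopt it, and the title, which names backslapping only, points elsewhere.
2. Union rate looks like the leading outcome: the title is about union rates and the hypothesis puts rate first. Time to union may therefore be secondary, which lowers the stakes. The documents still declare neither as main.
3. The SAP never mentions time to union, and the lack of adjustment is read from silence. Both are true. But a duration in months is a continuous variable, and no other test in the SAP fits it.

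A reader might infer two stronger points, which the documents do not support. One is that the trial has a 9% error rate as a matter of fact; that holds only if either comparison alone counts. The other is that union rate has the same two-sample defect. Fisher's exact test can be run on a three-by-two table, so this defect is confined to time to union. If union rate is instead tested pair by pair, it needs the same success rule.

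**Conclusion.** The point holds in conditional form. The stated test and threshold do not define a three-arm analysis of time to union. If either comparison is allowed to count, the false-positive risk is about 9% (8.5% to 9.5% if C is between half and twice the size of the other arms). It is about 5% if A and B are pooled. If both comparisons must succeed it is at most 5%, and about 0.9% when all arms are equal. The 9.1% figure needs roughly equal arms and large-sample normal theory but no assumed arm size; the simulated ranges rest on assumed arm sizes, union rates and visit distributions. All figures are two-sided, so they do not depend on the direction meant by the hypothesis. This should be fixed, and confidence is higher that the rule is missing than that the error is in fact inflated.

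**What to change.** In the Statistical Analysis Plan:

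- Name C vs A and C vs B as the two main comparisons on time to union, each by Mann-Whitney U, with patients not united by 52 weeks ranked last.
- State the success rule. If either comparison alone can support the claim, apply Holm: the smaller p value against 0.025 and, if that passes, the other against 0.05. If C must beat both, or A and B are pooled, state that before analysis; no adjustment is then needed.
- A Kruskal-Wallis test at 0.05 before the pairwise tests is an acceptable alternative to Holm. It also responds to A vs B, which is not in the hypothesis, and so loses slightly more power when B lies midway.
- State how union after exchange rodding or bone grafting (Data Points, item 16) is counted in the ranking.
- State how patients without a 52-week status are handled. The inclusion criterion "Complete radiographic and clinical follow-up for minimum one year" cannot be confirmed at enrolment.
- Name union rate as the main outcome, as the title and hypothesis suggest, and time to union as secondary, or state the reverse. Apply the same success rule to the Fisher comparisons.

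This takes a few sentences and no new data. Under the either-counts rule, power for C vs A falls from 80% to about 76% if A equals B, and to about 72% (Holm) or 70% (three-group test first) if B lies midway. The both-must-win rule needs no adjustment but is harder to meet, since two tests must succeed. The effect on sample size cannot be worked out, because the documents give no arm size. If the data have already been analysed, report both comparisons with Holm-adjusted p values and say that the rule was set afterwards.
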